#### **4.1.3 Exclusion Criteria**

1. Any mental condition of such that patient is unable to understand the nature, scope, and possible consequences of the study.
2. Evidence of active hepatitis B infection at screening.
3. Patients with untreated hepatitis C, or tuberculosis. Patients who have history of PML or known to be HIV positive, per standard care.
4. Any persistent or severe infection.

5. Pregnancy or lactation.
6. Significant, uncontrolled somatic disease or severe depression in the last year.
7. Current use of immunosuppressive medication, lymphocyte-depleting agents, or lymphocyte-trafficking blockers.
8. Patients with any significant comorbidity that in the opinion of the investigator, would interfere with participation in the study.
9. Any known allergy or inability to tolerate diphenhydramine or cetirizine.

#### **4.2 METHOD OF TREATMENT ASSIGNMENT**

Randomization will be based on a computer-generated sequence using a permuted block design with block size equal to four. Participants will be allocated in a 1:1 ratio of oral diphenhydramine to oral cetirizine. All patients on this study will receive OCR as part of their standard care.

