## **3. STUDY DESIGN**

### **3.1 DESCRIPTION OF THE STUDY**

This 6-month randomized controlled pilot study will determine whether there is some evidence that cetirizine is better tolerated than diphenhydramine without an increase in IRRs. Fifty-two patients, 26 patients per arm, will be randomized in a 1:1 ratio to receive cetirizine or diphenhydramine as premedication prior to OCR infusions on day 0 (1st half dose of 300mg), day 14 (2nd half dose of 300mg) and week 24 (1st full dose of 600mg). Neurological exams and the estimated Expanded Disability Status Scale (EDSS) will be obtained at screening and week 24, as well as premature termination visits, if applicable. Stanford Sleepiness Scale (SSS), and the Visual Analog Scale – Fatigue (VAS-F) will be administered at screening, baseline, day 14, and week 24. Modified Fatigue Impact Scale (MFIS) and Multiple Sclerosis Impact Scale (MSIS-29) will be administered at screening and week 24. MSIS-29 and MFIS will also be administered at premature termination, if applicable. Treatment Satisfaction Questionnaire for Medication (TSQM) will be administered at baseline, day 14, and week 24. TSQM, SSS, and VAS-F will be administered within 2 hours after each OCR infusion, followed by a phone call on the next business day following each infusion to collect and assess infusion reactions or other AEs.

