### **3.2 RATIONALE FOR STUDY DESIGN**

Shortly after the approval of OCR, we followed the premedication protocol used in OPERA I and II which included 100mg of methylprednisolone, 1 gram of acetaminophen, and 50mg of IV diphenhydramine. However, many patients experienced extreme sedation which caused severe drowsiness and impaired their ability to function, drive, or work during and after the infusion, and even the following day. As a result, we have decreased the dose of diphenhydramine to 25mg administered either IV or orally which has resulted in less, but still marked, drowsiness. Newer antihistamines such as cetirizine may be better tolerated; however, there is no evidence that they will be as effective in minimizing infusion reactions.

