#### **4.3. STUDY TREATMENT**

Patients will be enrolled and randomized to either the diphenhydramine or the cetirizine arm to be administered before their OCR doses, after informed consent and screening assessment have been completed. The premedication and OCR will be paid for by the patient or by the patient's insurance. Patients may receive any generic products of cetirizine or diphenhydramine that are available at their infusion center and do not require the same brand of the premedication for their subsequent infusions. The same brand does not need to be used at each OCR infusion, per patient.

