#### **Visit 2 or Baseline Visit (Day 0)**

- Concomitant medications and adverse events
- Eligibility review (can be done day -7 to day 0)
- Randomization for premedication arm (can be done day -7 to day 0)
- Administration of premedication and OCR (300mg)
- Infusion reaction assessment
- TSMQ (Administered within 2 hours after OCR infusion, may be completed via phone)
- SSS (Administered within 2 hours after OCR infusion, may be completed via phone)
- VAS-F (Administered within 2 hours after OCR infusion, may be completed via phone)
- Phone Call (next business day) to assess infusion reactions and any other AEs

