### **b. Secondary Endpoints**

The proportion of patients with IRRs during or after infusion will be compared using Fisher's exact tests at day 14 and week 24, as we expect the proportion of IRRs to be small at these time points based on OPERA I and II. Additionally, the proportion of IRRs after each infusion will be plotted overall and by severity for the two arms. At day 0, day 14, and week 24, TSQM scores will be compared between arms using Wilcoxon Rank Sum or two-sample t-tests, as appropriate based on normality, and SSS and VAS-F scores will be compared using Wilcoxon rank sum tests. MFIS, physical MSIS-29, and psychological MSIS-29 will be compared at week 24 using multiple linear regression with analysis of covariance (ANCOVA), adjusting for the screening score.

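### Section 4.2 prints one fixed block size of four, with no masking or concealment described; at worst a third of allocations are certain in advance, and varied, undisclosed blocks with concealed release would remove most of that certainty

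*Combined protocol and SAP*

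**What the plan says.** Section 4.2 is the whole of the assignment method: a computer-generated sequence, 1:1 allocation, "using a permuted block design with block size equal to four". No stratification factor is named. The section does not say who holds the sequence, how an assignment is released, or whether enrolling staff can see it.

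No masking of patients, treating staff or reaction assessors is described in the text reviewed, which did not include the title pages. The word blinded occurs only in the template pregnancy form in Appendix C. On supply, section 4.3 says: "Patients may receive any generic products of cetirizine or diphenhydramine that are available at their infusion center".

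Section 4.3 places randomization after consent and screening. The Visit 2 list in section 4.5.1 gives the second eligibility review and randomization the same window: "Randomization for premedication arm (can be done day -7 to day 0)". One exclusion criterion in section 4.1.3 rests on judgement: "Patients with any significant comorbidity that in the opinion of the investigator, would interfere with participation in the study". Sections 6.7 and 6.8 mention sites in the plural, but nothing says how many sites there are or whether they share one list.

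**The concern.** With a known block size of four, anyone who can follow past assignments in order knows the fourth allocation of every block, and the third whenever the first two match. Without masking, past assignments may be visible; without described concealment, nothing in the plan keeps them from the person deciding whether the next patient enters. Because entry depends partly on opinion, foreknowledge could influence who is enrolled and when, which randomization is meant to prevent.

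Section 3.2 gives reasons to steer in both directions. The team reduced diphenhydramine to 25mg, "which has resulted in less, but still marked, drowsiness", which could favor holding tired patients for cetirizine. The same section says there is no evidence that newer antihistamines protect equally well against infusion reactions, which could favor keeping reaction-prone patients off cetirizine.

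**Working it through.** **Inputs.** Block size 4 and 1:1 ratio (4.2); 52 patients, 26 per arm (3.1), which is 13 complete blocks; 25% reaction rate in each arm, margin -0.30, one-sided 0.05, 80% power (4.9.3, 4.9.6).

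**The plan's own figure.** n per arm = (1.645 + 0.842)² × 2 × 0.25 × 0.75 / 0.30² = 25.76, rounded up to 26. The stated sample size reproduces.

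**Fixed block of four, one list, all past assignments seen in order.** There are six equally likely blocks.
- Certain in advance: the 4th place always; the 3rd when the first two match (2 of 6 blocks). Expected number per block = 1 + 1/3 = 4/3, so 33.3%, or 52/3 = 17.3 patients. The count is 13 + Binomial(13, 1/3): at least 13, with 5th to 95th percentile 15 to 20.
- Best guess correct: 1/2 + 2/3 + 2/3 + 1 = 17/6 per block, so 70.8%, against 50% under simple randomization.

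**List shared by K equal-sized sites, each seeing only its own assignments but knowing block positions.**
- K = 2: 3rd place (1/4)(1/3) = 1/12; 4th place 1/8 + (3/8)(1/3) = 1/4. The sum, 1/3 per block, gives 8.3%, or 4.3 of 52. Best guess 60%.
- K = 3: 3rd place (1/9)(1/3) = 1/27; 4th place 1/27 + (2/9)(1/3) = 3/27. The sum, 4/27 per block, gives 3.7%, or 1.9 of 52. Best guess 57%.
- If sites do not know block positions, simulation gives 0% certain and a best guess of 59% (K = 2) or 56% (K = 3).

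**Randomly varying blocks, one list.** Simulated lists of 52 with sizes equally likely. The observer sees everything in order and knows the set of sizes but not their sequence.

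| Sizes | Certain | Best guess |
|---|---|---|
| 4 only | 33.3% | 70.8% |
| 4, 6 | 5.6–5.7% (2.9 of 52) | 69.0–69.1% |
| 4, 6, 8 | 2.3% (1.2 of 52) | 67.7% |
| 2, 4 | 11.0% | 72.1% |
| 2, 4, 6, 8 | 2.0% | 68.5% |

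Across the common mixes tried, the certain share is 2.0% to 11.0%. If the set of sizes is unknown and unbounded, nothing is strictly certain.

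**Seven blocks of four and four of six in random order** (28 + 24 = 52): about 8% certain (4.0 of 52) and 70% guessed, even if the composition is known; always 26/26.

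**Balance and power.** With independently drawn sizes the last block may be cut at patient 52. Sizes 4/6 give 26/26 in 77% of lists and 27/25 in 23%. Sizes 4/6/8 give 26/26 in about 73%, 27/25 in about 27%, and 28/24 in roughly 0.2 to 0.3%. Exact power at 25% versus 25%, using a Wald interval because section 4.9.3 names no method: 82.0% at 26/26; 81.4% or 81.8% at 27/25, depending on which arm is larger; 80.0% or 80.8% at 28/24.

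**The case against.** The strongest reply is that one third is a worst case. It needs one list and an enroller who sees every assignment in order. Randomization can precede infusion by up to seven days, so watching infusions does not reveal the order. Acting on a prediction means deferring or declining a patient already consented and screened, and exclusion 9 already removes those known not to tolerate either drug. All of this stands, and it is why 33% is an upper figure and not an estimate for this trial.

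A second reply is that varied blocks barely reduce guessing. With sizes 4 and 6, the excess over chance falls only from 20.8 to about 19 points. This also stands: varied blocks remove most certain knowledge but not most guessing, so concealed release belongs in the fix. Concealment does not hide earlier assignments that are already openly known, so the two measures complement each other.

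A third reply is that fixed blocks of four are a legitimate choice that guarantees 26/26 in a small pilot. That is true, but a fixed mix of block sizes gives the same guarantee at 52.

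A reader might go further and infer a bias against cetirizine on tolerability. The study asks "whether there is some evidence that cetirizine is better tolerated than diphenhydramine without an increase in IRRs"; the plan says "SSS and VAS-F scores will be compared using Wilcoxon rank sum tests", without adjustment, whereas MFIS and MSIS-29 "will be compared at week 24 using multiple linear regression with analysis of covariance (ANCOVA), adjusting for the screening score". Tired patients steered to cetirizine would worsen its sleepiness and fatigue scores. The documents do not support that direction, because section 3.2 also supplies the opposing motive and nothing shows that either was acted on.

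**Conclusion.** The point holds as a design weakness that is cheap to remove. The fixed, printed block of four makes up to 33% of allocations certain (about 17 of 52) and 71% guessable, assuming one list with all past assignments seen in order. If equal-sized sites share the list and see only their own patients, the certain share is about 0 to 8% with two or three sites. The documents do not settle which case applies.

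These figures measure predictability, not bias. They give no size or direction for any bias, and no effect on the primary or any secondary endpoint is shown. Nor is the improvement to about 6% a property of varied blocks in general: it belongs to sizes 4 and 6, equally likely, with the set known to the observer. The sample size calculation is unaffected.

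**What to change.** In section 4.2:

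1. Replace the fixed block of four with randomly varying block sizes, for example 4 and 6. A mix of 2 and 4 is a poor choice, since its best-guess rate (72.1%) exceeds that of the fixed block.
2. Keep the sizes in a document held by the statistician, not in the protocol.
3. State that each assignment is released from a list concealed from enrolling staff, and only after the final eligibility review is recorded. Name who holds the list and whether sites share it.

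Cost: a regenerated list, a short change to section 4.2, and IRB approval of the amendment before implementation (section 3.5). If enrollment has begun, only assignments not yet made can change. With independently drawn sizes 4 and 6, about 23% of lists end 27/25, at a cost of 0.6 percentage points of power or less (81.4 to 81.8% against 82.0%). If exact balance is wanted, use seven blocks of four and four of six in random order; this gives 26/26 provided exactly 52 are randomized.

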#### **4.3. STUDY TREATMENT**

Patients will be enrolled and randomized to either the diphenhydramine or the cetirizine arm to be administered before their OCR doses, after informed consent and screening assessment have been completed. The premedication and OCR will be paid for by the patient or by the patient's insurance. Patients may receive any generic products of cetirizine or diphenhydramine that are available at their infusion center and do not require the same brand of the premedication for their subsequent infusions. The same brand does not need to be used at each OCR infusion, per patient.

##### **4.3.1 Packaging, Preparation, Storage, Handling, Dosage, and Administration**

###### Packaging, Preparation, Storage and Handling

The study team is not responsible for collecting or reviewing data on how the premedications or OCR were packaged, prepared, stored, or handled for the purposes of this trial.

The treating physician will refer to the specific prescribing information provided by the drug manufactures for detailed instructions on packaging, preparation, storage, and handling for both the premedications and OCR^4. The standard of care process is to be followed.

###### Dosage and Administration

1. Patients will be randomized to either diphenhydramine 25mg orally or cetirizine 10mg orally. The patients randomized to diphenhydramine will receive diphenhydramine 25mg orally 30-60 minutes prior to each OCR infusion. The patients randomized to cetirizine will receive cetirizine 10mg orally 30-60 minutes prior to each OCR infusion.

The treating physician will refer to the specific prescribing information provided by the drug manufactures for detailed instructions on administration of the premedications. The standard of care process is to be followed.

2. OCR 300mg IV will be given on Day 0 and repeated with the same dose on Day 14±2. Patients will then receive OCR 600mg IV at 24 weeks.

Although OCR may be administered on an outpatient basis, patients may be hospitalized for observation at the discretion of the investigator. OCR infusions should always be administered in a hospital or clinic environment under close supervision of the investigator or a medically qualified staff member.

The treating physician will refer to the OCR prescribing information for detailed instructions on administration. The standard of care process is to be followed.

#### **4.3.2 Dosage Modification**

Dose modifications of diphenhydramine or cetirizine are not permitted. See section 3.4 for dose modifications of OCR in the case of IRRs.

#### **4.4 CONCOMITANT AND EXCLUDED THERAPY**

All concomitant medications are allowed except immunosuppressants, lymphocyte-depleting agents, or lymphocyte-trafficking blockers while patients are receiving OCR. All medications including over-the-counter medication and supplements will be recorded at each clinical visit. At screening, all medications taken 4 weeks prior to screening will be reviewed and recorded, as well as all prior lifetime MS disease modifying therapies taken by the patient.

#### **4.5 STUDY ASSESSMENTS**

Informed consent must be obtained before proceeding with the study assessments. See section 6.2 for the detailed description of the informed consent process.

##### **4.5.1 Assessments during Treatment**

###### **Visit 1 or Screening Visit (-28 to -1 days prior to Baseline)**

- Informed consent
- Eligibility review
- Demographic information
- Review of disease and medical history
- Review of prior and concomitant medications, including lifetime MS disease modifying therapy history
- Reason(s) for switching to OCR
- Vital signs (blood pressure, heart rate, oral temperature, weight, and height)
- Neurological exam (may be historical exam if completed within 28 days prior to consent)
- Confirmation of estimated EDSS of 0 to 6.5, inclusive
- Laboratory assessments:
  - Urine or serum pregnancy test (females of childbearing potential only)
  - CBC and LFTs (may be historical laboratories if completed within 28 days prior to consent)
  - Hepatitis B testing (may be historical laboratories if completed within 6 months prior to consent)

- Serum immunoglobulins, quantitative (may be historical laboratories if completed within 28 days prior to consent)
- SSS
- VAS-F
- MFIS
- MSIS-29
- Adverse events

#### **Visit 2 or Baseline Visit (Day 0)**

- Concomitant medications and adverse events
- Eligibility review (can be done day -7 to day 0)
- Randomization for premedication arm (can be done day -7 to day 0)
- Administration of premedication and OCR (300mg)
- Infusion reaction assessment
- TSMQ (Administered within 2 hours after OCR infusion, may be completed via phone)
- SSS (Administered within 2 hours after OCR infusion, may be completed via phone)
- VAS-F (Administered within 2 hours after OCR infusion, may be completed via phone)
- Phone Call (next business day) to assess infusion reactions and any other AEs

#### **Visit 3 (Day 14 +/- 2 days from baseline)**

- Concomitant medications and adverse events
- Administration of premedication and OCR (300mg)
- Infusion reaction assessment
- TSMQ (Administered within 2 hours after OCR infusion, may be completed via phone)
- SSS (Administered within 2 hours after OCR infusion, may be completed via phone)
- VAS-F (Administered within 2 hours after OCR infusion, may be completed via phone)
- Phone Call (next business day) to assess infusion reactions and any other AEs

#### **Visit 4 (24 weeks +/- 14 days from baseline)**

- Vital signs (blood pressure, heart rate, oral temperature, and weight)
- Neurological exam (must be completed pre-OCR infusion)
- Estimated EDSS (must be completed pre-OCR infusion)
- Concomitant medications and adverse events (AE reporting period continues 30 days following the last administration of study treatment or study discontinuation/termination, whichever is earlier. Reassess AEs via phone call at 30 days +7 from time of last dose or study termination.)
- Laboratory assessments:
  - Urine pregnancy test (females of childbearing potential only, if positive, confirm by serum pregnancy test)
  - CBC and LFTs
  - Serum immunoglobulins, quantitative
- Administration of premedication and OCR (600mg)
- Infusion reaction assessment

- TSMQ (Administered within 2 hours after OCR infusion, may be completed via phone)
- SSS (Administered within 2 hours after OCR infusion, may be completed via phone)
- VAS-F (Administered within 2 hours after OCR infusion, may be completed via phone)
- MFIS
- MSIS-29
- Phone call (next business day) to assess infusion reactions and any other AEs

### **Premature Termination Visit**

If OCR or the premedication is withdrawn and the patient is unwilling to continue in the trial for observation, complete a premature termination visit as soon as possible. If the patient discontinues from the study for any other reason noted in the patient discontinuation criteria, a premature termination visit must be performed as soon as possible. Patients who were withdrawn from the study for any reason will not be replaced. The following clinical and laboratory evaluations will be performed:

- Vital signs (blood pressure, heart rate, oral temperature, and weight)
- Neurological exam
- Estimated EDSS
- MFIS
- MSIS-29
- Concomitant medications and adverse events (AE reporting period continues 30 days following the last administration of study treatment or study discontinuation/termination, whichever is earlier. Reassess AEs via phone call at 30 days +7 from time of last dose or study termination.)
- Laboratory assessments:
  - CBC and LFTs
  - Serum immunoglobulins, quantitative
- Primary reason for discontinuation

### **Lost to Follow-up**

If a patient is lost to follow-up, she/he will be withdrawn from the study. Appropriate means of contact to consider lost to follow-up are 3 documented phone attempts and 1 certified letter.

## **4.6 DISCONTINUATION OF THERAPY**

1. Diphenhydramine or cetirizine must be discontinued for any of the following reasons:
  - Life-threatening or serious hypersensitivity reaction
  - Patient discontinues OCR therapy
  - Patient election to discontinue therapy (for any reason)
2. OCR therapy must be discontinued for any of the following reasons:
  - Life-threatening IRR or serious hypersensitivity reaction
  - Active hepatitis B infection
  - PML
  - Active TB, either new onset or reactivation
  - HIV

- Patient becomes pregnant
- Unacceptable toxicity
- Multiple serious infections
- Patient election to discontinue therapy (for any reason)

#### **4.7 PATIENT DISCONTINUATION**

Patients may be withdrawn from the study for any of the following reasons:

- Patient withdraws consent
- Patient is unwilling or unable to comply with the protocol
- Physician's discretion

#### **4.8 STUDY DISCONTINUATION**

Genentech, Inc. and the Principal Investigator have the right to terminate this study at any time. Reasons for terminating the study may include the following:

- Patient enrollment is unsatisfactory
- Data recording are inaccurate or incomplete
- Study protocol not followed

#### **4.9 STATISTICAL METHODS**

##### **4.9.1 Analysis of the Conduct of the Study**

For the primary, non-inferiority endpoint, analysis will be on both the intention-to-treat and per-protocol populations (two-sample proportion non-inferiority test). Analysis for secondary endpoints will be on the intention-to-treat population. The intention-to-treat population is defined as all randomized patients, and the per-protocol population will be those who completed the study as per protocol specification.

If the study is terminated before planned enrollment is reached, only descriptive analysis will be performed.

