### **3.3 OUTCOME MEASURES**

#### **3.3.1 Primary Outcome Measure**

The proportion of patients having an infusion-related reaction, as defined by the Common Terminology Criteria (CTCAE), version 4 during or after the first-half dose of the first infusion on day 0. Infusion-related reactions will be documented at the infusion clinic on the day of the infusion and reported by the patient at the follow-up phone call the next business day after the infusion.

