##### **4.9.3 Efficacy Analysis**

###### **a. Primary Endpoint**

The proportion of patients with IRRs during or after the first infusion on day 0 will be reported for each arm. Cetirizine will be considered non-inferior to diphenhydramine if the lower limit of the two-sided, 90% confidence interval for the difference in proportions (diphenhydramine-cetirizine) is greater than the non-inferiority margin of -0.30^5.

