#### **4.9.5 Missing Data**

Baseline characteristics and outcomes for patients who followed protocol and completed the study, violated protocol, and discontinued the study will be reported separately. The reasons for discontinuing or violating protocol will be reported and any influence on the trial results will be discussed. Any other irregularities that result in missing data will be fully identified and discussed.

For the primary endpoint using the intention-to-treat population, the missing data mechanism will be examined and multiple imputation or best/worst imputation will be used, assuming missing at random. For the primary endpoint, assessed at day 0, we expect missing data will be limited.

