#### **4.9.6 Determination of Sample Size**

Based on the results of the OPERA I and II trials, we assume that 25% of patients in the diphenhydramine arm and 25% of patients in the cetirizine arm will experience mild to severe IRRs during or after receiving the first infusion on day 0. Assuming that a 30% absolute difference (i.e. margin = - 0.30) in the proportion of patients with IRRs between premedication groups is the maximum relevant difference when holding that cetirizine is not inferior to diphenhydramine, 26 patients per arm are needed to achieve 80% power with a one-sided significance level of 0.05. As this is a pilot study, we allow a large margin to establish some evidence of non-inferiority. The two-sample proportion test for non-inferiority in the R package Trial Size was used for the calculation.

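### The per-protocol set for a day-0 endpoint is defined by completing the 24-week study, and no rule says which analysis set decides non-inferiority

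*Combined protocol and SAP*

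**What the plan says.** Section 4.9.1 puts the primary non-inferiority test on two populations. ITT is everyone randomized; for the other, "the per-protocol population will be those who completed the study as per protocol specification". The same section adds: "Analysis for secondary endpoints will be on the intention-to-treat population". The PP set therefore serves the primary endpoint alone.

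Section 3.3.1 fixes that endpoint as an infusion-related reaction (IRR) "during or after the first-half dose of the first infusion on day 0", documented in the clinic and at the call on the next business day. The study itself runs about 6 months, with its last infusion visit at week 24 (sections 3.1 and 4.5.1).

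Between those two points a patient may leave by choice, by withdrawing consent or at the physician's discretion (sections 4.6 and 4.7). One listed reason for stopping ocrelizumab is "Life-threatening IRR or serious hypersensitivity reaction". Leaving the study is not automatic: the premature termination visit in section 4.5.1 applies when treatment is withdrawn and "the patient is unwilling to continue in the trial for observation".

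The decision rule in section 4.9.3a reads "Cetirizine will be considered non-inferior to diphenhydramine if the lower limit of the two-sided, 90% confidence interval" for the difference lies above -0.30. It names no population. Section 4.9.5 promises that results for "patients who followed protocol and completed the study, violated protocol, and discontinued the study will be reported separately", with discussion of any influence on the trial results.

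**The concern.** A per-protocol analysis in a non-inferiority trial is there to check that protocol deviations have not made the arms look alike. Here it selects patients on events after the outcome. Someone who took the assigned antihistamine, had the day-0 infusion and was fully assessed can be removed because of a pregnancy or a change of mind months later, or because the reaction itself led to stopping. The last route ties membership of the set to the endpoint being compared.

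The bias can go either way. It favours non-inferiority if patients with reactions are lost more often on cetirizine, or equally often in both arms when cetirizine is truly worse. It works against non-inferiority if they are lost mainly on diphenhydramine. It vanishes if loss is unrelated to reactions.

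Two gaps add to this. The plan does not say whether a patient who stops treatment but stays for observation has completed the study as specified, so membership could be settled after outcomes are known. Nor does it say what is concluded if one set meets the margin and the other does not.

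**Working it through.** **1. The plan's own figure.** Section 4.9.6 says "26 patients per arm are needed to achieve 80% power with a one-sided significance level of 0.05", with 25% reactions in each arm and a margin of -0.30. The unpooled normal formula gives

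n = [0.25×0.75 + 0.25×0.75] × (1.645 + 0.842)² / 0.30² = 0.375 × 6.183 / 0.09 = 25.76, rounded up to 26 per arm.

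The sample size is reproduced and is not in question.

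**2. The decision rule in ITT.** The plan does not name an interval method; I used the Wald limit

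L = p_D − p_C − 1.645 × √[p_D(1−p_D)/n_D + p_C(1−p_C)/n_C], with non-inferiority if L > -0.30.

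Exact binomial enumeration with 26 per arm gives 82.0% power at 25%/25% and 4.87% false non-inferiority at the margin (25% diphenhydramine, 55% cetirizine).

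**3. The rule in the PP set.** Suppose a patient with an IRR is lost with probability a (which may differ by arm) and one without with probability b. The reaction rate among those retained is

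p′ = p(1−a) / [p(1−a) + (1−p)(1−b)].

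Example with a = 10% on diphenhydramine, 30% on cetirizine, and b = 5%:

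- diphenhydramine: 0.225 / (0.225 + 0.7125) = 0.240
- cetirizine: 0.385 / (0.385 + 0.4275) = 0.474
- expected difference: -0.234, against a true -0.300.

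Exact enumeration over reactors kept, non-reactors kept and patients dropped, at the margin:

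| IRR patients lost, D / C | Others lost | Expected PP difference | PP false non-inferiority |
|---|---|---|---|
| 10% / 10% | 10% | -0.300 | 4.8% |
| 5% / 5% | 0% | -0.297 | 5.1% |
| 10% / 10% | 5% | -0.297 | 5.1% |
| 20% / 20% | 5% | -0.288 | 6.0% |
| 30% / 30% | 5% | -0.277 | 7.2% |
| 30% / 30% | 0% | -0.272 | 7.9% |
| 10% / 20% | 5% | -0.267 | 8.1% |
| 10% / 30% | 5% | -0.234 | 12.5% |
| 20% / 10% | 5% | -0.317 | 3.7% |
| 30% / 10% | 5% | -0.339 | 2.5% |

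All loss rates are assumptions; the documents give none.

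**4. What the missing decision rule is worth.** Enumerating both sets jointly over the same patterns:

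- the two verdicts differ in 1.2% to 8.1% of trials at the margin, and in 3.2% to 13.5% at 25%/25%;
- a claim made when either set passes is false in 5.2% to 12.7% of trials;
- a claim made only when both pass is false in 2.2% to 4.6%.

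Loss of 10% unrelated to reactions does not bias the PP set, yet the verdicts still differ in 8.1% of trials at 25%/25%.

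**5. One patient is enough.** Counts are diphenhydramine versus cetirizine.

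| Table | Difference | Wald limit | Newcombe limit | Verdict |
|---|---|---|---|---|
| ITT 6/26 vs 9/26 | -0.115 | -0.320 | -0.309 | fails |
| PP 6/26 vs 8/25 (one cetirizine reactor lost) | -0.089 | -0.294 | -0.285 | passes |
| ITT 7/26 vs 9/26 | -0.077 | -0.287 | -0.276 | passes |
| PP 6/25 vs 9/26 (one diphenhydramine reactor lost) | -0.106 | -0.314 | -0.302 | fails |

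Both reversals hold under either interval.

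**The case against.** The strongest reply is about size. With loss of 10% or less and equal by arm, PP false non-inferiority is 4.8% to 5.1%, which is no practical change. The larger figures need 20% or more of reactors to leave, or reactors to leave one arm two or three times as often as the other. Nothing in the documents predicts that: the introduction says most reactions were mild to moderate, and the only stops forced by a reaction are for life-threatening or serious ones. This stands, so the upper figures are worst cases and not forecasts. Reactors may still choose to stop after a milder event, at an unknown rate.

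Second, ITT is analysed and unaffected, and section 4.9.5 would make selective loss visible. That also stands, but describing a disagreement does not settle it.

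Third, analysing both sets may be read as requiring both to pass. That is a sensible reading, and it keeps the error below 5%. But section 4.9.1 says where the test is run, not how the claim is decided.

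Fourth, near-margin reversals depend on the interval. For example, 6/26 vs 8/26 becoming 5/25 vs 8/26 reverses under Wald (-0.279 to -0.306) but not under Newcombe (-0.270 to -0.297). That is true of this table; the two reversals shown in the working do not depend on the choice.

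Finally, this is a pilot seeking some evidence, with a deliberately wide margin. It nonetheless states a formal test, margin, significance level and power.

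**Conclusion.** The concern holds. As written, the PP set can discard observed day-0 outcomes because of later events, including events caused by the outcome, and no endpoint needs that restriction. The effect on PP false non-inferiority is negligible under light, balanced loss and runs from 2.5% to 12.5% under the heavier or unbalanced patterns examined, against 4.9% for ITT. These figures assume the Wald interval, 26 per arm, and loss rates that are mine and not the plan's. The absence of a deciding rule does not depend on those assumptions. ITT remains valid, so the trial is not undermined, but its check is mis-specified and its verdict can be ambiguous. This should be fixed before analysis.

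**What to change.** Replace the PP definition in section 4.9.1 with wording such as:

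> For the primary endpoint, the per-protocol population is all randomized patients who met eligibility, took the assigned antihistamine and the other required premedication as specified for day 0, started the day-0 ocrelizumab infusion, and had IRR status assessed through the follow-up call. Nothing after that call excludes a patient.

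Then state how the two sets decide the claim. One option:

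> Non-inferiority is concluded only if the rule in 4.9.3a is met in both populations. If only one meets it, both are reported and the result is called inconclusive.

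Naming ITT as decisive, with PP as supportive, would also close the gap; what matters is that the choice is made beforehand.

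The cost is a few sentences. N stays at 26 per arm and no other endpoint uses the PP set. Two points need attention. If premedication timing is to count as compliance, the team should confirm that administration times are recorded, because the documents do not say so. A both-must-pass rule also lowers power: if 5% to 10% of patients fail the day-0 criteria for reasons unrelated to reactions (assumed), joint power at 25%/25% is 78.2% to 75.7%, against 82.0% for ITT alone and a design target of 80%.
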